### Aims

The first aim of this study is to highlight possible psychosocial clusters of variables that are specific to the onset and maintenance for each condition (FM, CM, and VU). Specifically, the observation of possible clusters will be made based on variables such as personality traits, defense mechanisms, central sensitization, and childhood traumatic experiences. The hypothesis is that specific psychological factors (clusters of high number of early traumatic events, high levels of central sensitization, and specific traits and defense mechanisms) characterize FM, CM, and VU groups compared to controls reporting other types of CP (e.g., knee arthrosis, rheumatoid arthritis).

A second aim, to give directions for tailored psychological treatments devoted to these conditions, is to explore the association between FM, CM, and VU with depression, anxiety, somatization, quality of life, alexithymia, social support, sexual satisfaction, and functioning. In line with our hypothesis that each of

these conditions has specific areas of psychological sensitivity, this will make it possible to identify specifically for each condition the areas of greatest interest that can be investigated and treated in clinical intervention.

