### *Self-report questionnaires*

#### *Main questionnaires (all the participants are requested to complete them)*

- Highly Sensitive Person Scale (HSP-12) (Aron & Aron, 1997; Lionetti et al., 2018): this questionnaire investigates the theoretical framework of Sensory Processing Sensitivity, referring to a temperamental trait that predisposes to a broader sensory processing of information captured by a variety of indicators, rather than simple sensitivity to sensory stimuli. The questionnaire reports a total sensitivity score and 3 sub-factors (Easy of Excitation (EOE), Aesthetic Sensitivity (AES) and Low Sensory Threshold (LST)).
- Central Sensitivity Inventory (CSI) (Chiarotto et al., 2018): The Central Sensitisation Inventory was developed to assess the overlapping symptomatic dimensions of the central sensitivity syndrome. This measure is intended as a screening tool to help identify the presence of the syndrome and to alert clinicians that presenting symptoms may be related to it. It consists of two parts: part A provides a 0-100 total score for 25 items on current health symptoms with five response options ranging from 'never' (0) to 'always' (4); part B investigates if patients were previously diagnosed by a physician with one or more of seven different conditions.
- Traumatic Experiences Checklist (TEC) (Nijenhuis et al., 2002): the instrument investigates 29 types of potential trauma, including the events listed in criterion A of PTSD, as well as other potentially overwhelming events: loss of significant others, life-threatening illness or aggression, experience of warehousing, emotional neglect, emotional abuse, physical abuse, sexual harassment and sexual trauma. The questionnaire includes a total complex trauma score and 5 subscales investigating emotional neglect, emotional abuse, physical threat, sexual harassment, and sexual abuse.
- PID-5 Short form (Thimm et al., 2016): This instrument represents the short version of the PID-5 self-report inventory designed to assess the 25 facets of pathological personality traits and the five higher-order domains of DSM-5 Criterion B. It assesses 5 personality trait domains including negative affect, detachment, antagonism, disinhibition, and psychotism, with each trait domain consisting of 5 items.

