- Defense Mechanism Rating Scales - DMRS-SR-30 (Di Giuseppe et al., 2020); is an instrument based on the identification of 30 individual defenses arranged hierarchically in 7 levels according to similarity of function and level of adaptability. The DMRS provides a definition of each defense mechanism, a description of its intrapsychic function and criteria for discriminating one defense from its neighboring defenses. Defense levels can be categorized as mature and immature neurotic, and the latter is further subdivided into depressive and non-depressive.
- Mental Pain Questionnaire (Svicher et al., 2019): is a 10-item true-false style self-report questionnaire developed to assess mental pain.

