#### STATYSTICAL PLANNED ANALYSES

The required sample size was estimated a priori for the ANOVA procedure that tested the cluster model sensitivity having 4 groups (migraine, fibromyalgia, vulvodynia, and controls). Using the G\*power program,  $p = 0.05$ , statistical power of 85%, and effect size of 0.35, the calculation yielded a total sample size of  $n = 108$  participants per group (432 as total) The four centers involved in the recruitment of the participants will be the Università di Milano IRCCS Sant'Ambrogio Galeazzi under the head of [name] and Dott. [name], the IRCCS Mondino di Pavia under the head of [name] and [name], The Policlinico San Matteo of Pavia under the head of [name] and Dott. [name], and the Policlinico Umberto I of Sapienza University of Rome under the head of Dott. [name].

ANOVAs and  $\chi^2$  analyses will be carried out to compare groups on sociodemographic characteristics for descriptive reasons and to select possible covariates based on selection bias.

A group of cluster analyses will be performed to classify the samples based on personality traits, defense mechanisms, central sensitization, and childhood traumatic experiences (twenty-two variables corresponding to total scores and thematic subscales of the related measures), aiming to identify different clinical phenotypes within the study samples. A statistical procedure of Two-Step Cluster Analysis will be preferred due to its ability to ensure that one variable does not dominate the cluster solution. Furthermore, it enables the user to identify the importance of each item in the cluster solution. The model fit will be assessed by Schwarz's Bayesian Information Criterion and evaluated by the average silhouette coefficient, an internal validity index representing cluster cohesion and separation quality, ranging between 0 and 1; the closer to 1, the better the model.

Crosstab analyses will be performed to test the association and their strength, and MANOVAs to detect differences in the classification variables based on cluster groups, and Pearson's correlation to explore associations among clusters and other psychological domains. The statistical analyses will be performed using IBM SPSS v. 27.0 and AMOS v.22 (SPSS Inc., Chicago, IL, USA).

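### The 22 clustering inputs count trauma and defenses many times and central sensitization once or twice, so a group difference confined to central sensitization would rarely show

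*Combined protocol and SAP*

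**What the plan says.** The section headed STATYSTICAL PLANNED ANALYSES says the cluster analyses will "classify the samples based on personality traits, defense mechanisms, central sensitization, and childhood traumatic experiences". The inputs are given only as "twenty-two variables corresponding to total scores and thematic subscales of the related measures", without a list. Two-Step Cluster Analysis "will be preferred due to its ability to ensure that one variable does not dominate the cluster solution". The same section mentions the importance of each item, fit by BIC and silhouette, crosstabs, and MANOVAs of the classification variables by cluster. I read the crosstabs as diagnosis by cluster, although the plan does not say so.

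The main-questionnaires section describes these scores:

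- Central sensitization (CSI): "part A provides a 0-100 total score for 25 items on current health symptoms", while "part B investigates if patients were previously diagnosed by a physician with one or more of seven different conditions".
- Trauma (TEC): "The questionnaire includes a total complex trauma score and 5 subscales".
- Defenses (DMRS-SR-30): "30 individual defenses arranged hierarchically in 7 levels according to similarity of function and level of adaptability", with broader categories built from those levels.
- Personality (PID-5 short form): five domains.
- Sensitivity (HSP-12): a total and three sub-factors. The plan does not say whether these count as personality traits in the clustering.

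The Aims section expects "clusters of high number of early traumatic events, high levels of central sensitization, and specific traits and defense mechanisms" to mark the three pain conditions against controls with other chronic pain.

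**The concern.** Two-Step clustering adds up a distance contribution from each variable. If every variable has a similar say, a construct's influence grows with the number of scores it supplies. A safeguard against one dominant variable does nothing about six trauma scores or seven to ten defense scores that move together. Entering a total beside its own subscales adds to this, because the same answers are counted twice. BIC and silhouette are no protection: they measure internal fit, and a clean split on defenses alone could satisfy both.

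The measures section calls cluster analysis the study's main objective. If membership mostly follows the constructs with the most scores, a null diagnosis-by-cluster table could be taken as evidence that central sensitization does not separate the groups, when the clustering had little chance of showing it.

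**Working it through.** **1. Reproducing the count of 22.** From the scores described under Main questionnaires, several splits reach the stated number:

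| Split | CSI | TEC | PID-5 | HSP-12 | DMRS | Sum | TEC + DMRS |
|---|---|---|---|---|---|---|---|
| A | 1 | 6 | 5 | 0 | 10 (7 levels + 3 categories) | 22 | 16/22 = 73% |
| B | 1 | 6 | 5 | 3 | 7 | 22 | 13/22 = 59% |
| C | 1 | 5 | 5 | 4 | 7 | 22 | 12/22 = 55% |
| D | 2 (Part B scored) | 5 | 5 | 3 | 7 | 22 | 12/22 = 55% |

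So 22 can be reached, but not uniquely. A and B place the TEC total beside its subscales. C does the same with the HSP-12 total. D has no such overlap. A wider enumeration gave the CSI 1 or 2 inputs in every case, and trauma plus defenses 10 to 16 (45-73%).

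**2. Share of inputs.** CSI: 1/22 = 4.5%, or 2/22 = 9.1%. Equal weight for four constructs would be 1/4 = 25%.

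**3. How far clusters reflect the CSI.** Simulation of split A with N = 432 (the plan's total). The documents give none of the following, so they are assumptions: within-construct correlation 0.5; TEC total equal to the sum of its subscales; CSI 0.8 SD higher in the pain groups. There were 30 runs per cell. A diagonal normal mixture stood in for Two-Step; the four-score comparison (one score per construct) used k-means. Entries are the share of variance explained by cluster membership, for 2 / 3 / 4 clusters:

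| Between-construct r | CSI, 22 inputs | A defense category score, 22 inputs | CSI, four scores |
|---|---|---|---|
| 0 | 0.003 / 0.007 / 0.011 | 0.539 / 0.601 / 0.661 | 0.184 / 0.315 / 0.384 |
| 0.3 | 0.068 / 0.104 / 0.106 | 0.518 / 0.604 / 0.636 | 0.281 / 0.379 / 0.441 |
| 0.5 | 0.202 / 0.257 / 0.258 | 0.468 / 0.627 / 0.643 | 0.374 / 0.474 / 0.524 |

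The CSI is under-weighted in every row, and close to absent only at r = 0.

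**4. How often the crosstab is significant at 0.05.** Four groups of 108, diagonal mixture, 40 runs per cell unless noted:

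| True difference, pain groups vs controls | Clusters | 22 inputs | Four scores |
|---|---|---|---|
| CSI only, 0.8 SD | see below | 5-8% | 23-58% (separate set, 60 runs, 2 or 3 clusters) |
| Trauma and CSI, 0.6 SD | fixed at 2 or 3 | 8-55% | 78-92% |
| Trauma and CSI, 0.6 SD | chosen by BIC | 70-72% | 2% at r = 0.1; 78% at r = 0.3 |
| Specific traits and defenses | widest gap | 52% | 25% |

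With 40 runs, the Monte Carlo standard error at 5% is sqrt(0.05 × 0.95 / 40) = 3.4 points, so 5-8% cannot be told apart from the false-positive rate. Other settings (50 to 200 runs per cell) put the CSI-only figure at 2-12%. The trauma-plus-CSI figure moves much more. In another set with 2 or 3 fixed clusters it ran from 12% to 85%. With every trauma score shifted by the full 0.6 SD and BIC choosing the number of clusters, it was 86-97%.

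**The case against.** There is a serious case on the other side.

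- **The hypothesis is joint.** The Aims section does not predict a difference in central sensitization alone. For a joint trauma and CSI difference, the planned inputs can do well once BIC picks more than two or three clusters. If all four constructs differ by 0.4 SD, both approaches exceed 98%. This stands, and it limits the harm. One caveat is that the software's automatic rule may choose fewer clusters than minimum BIC.
- **Balancing has a price.** The Aims section speaks of specific traits and defenses. A single trait score and a single defense score can cancel opposite shifts, and neither instrument is described as having one overall score. At between-construct r = 0.1, BIC chose one cluster for the four-score version in 56 of 60 and 58 of 60 runs. This stands against making the balanced solution primary.
- **The inputs are inferred.** Split D has no total beside its parts, and overlap among defense scores arises only if categories join the levels. This stands. The TEC overlap is the firmest, because the plan names totals and subscales together.
- **The plan would show the problem.** Item importance and the MANOVAs would reveal a weak CSI contribution. They would not change membership or the crosstab. The sample-size paragraph mentions an ANOVA across the four groups but names no outcome, so it cannot be relied on as a direct CSI comparison.

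A reader might infer that the clusters barely register central sensitization, or that it is the marker on which the hypothesis rests. The documents support neither. They give no correlations, at r = 0.3-0.5 the CSI is visible in the clusters, and the Aims section lists it as one of four components.

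**Conclusion.** The concern holds in a limited form. On the scores described, central sensitization supplies 1 input of 22, or 2 at most, while trauma and defenses together supply roughly half to three quarters. The stated reason for Two-Step covers single variables, not constructs, and the plain reading of the input description counts trauma information twice. Central sensitization is therefore under-weighted, and a difference confined to it would reach the crosstab in about 5-8% of runs at 0.8 SD.

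It would be tempting to go further and say that the study will probably miss a nociplastic phenotype marked by trauma and central sensitization together. That does not follow: the result ranges from a large loss to almost none with the number of clusters, the correlations and the way the trauma shift is modelled, and the documents settle none of these. The simulated figures also rest on a mixture model that only approximates Two-Step, so they give direction and rough size. The change is worth making because it is cheap and bears on how a null result on a named construct would be read.

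**What to change.** - **Primary solution:** for each measure enter either the total or the subscales, not both. Apply the same rule to DMRS levels and the categories built from them. List every input by name, stating whether CSI Part B and the HSP-12 are included.
- **Sensitivity analysis:** prespecify a construct-balanced solution with equal weight for each of the four constructs and CSI Part A for central sensitization. Define the trait and defense scores in advance, and report the solution beside the primary one. Balance has to come from the number of inputs: under the log-likelihood distance, rescaling variables changes nothing.
- **Interpretation:** state that the primary crosstab alone will not be used to conclude that central sensitization fails to distinguish the groups.

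The cost is some SAP wording and one extra cluster run on data already being collected. The primary solution may have fewer than 22 inputs. The balanced solution should stay secondary, because composite trait and defense scores can hide opposite shifts and may yield no clusters under BIC.

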### PSYCHOLOGICAL FACTORS ASSOCIATED TO NP

As we have already pointed out separately for the three pathological conditions (chronic migraine, fibromyalgia, and vulvodynia), there is evidence that factors such as personality traits, defense mechanisms, central sensitization, and childhood traumatic experiences may contribute significantly to the genesis of these disorders through a process of central sensitization of pain pathways. Central sensitization (CS) is defined as increased responsiveness of nociceptive neurons in the central nervous system to their normal or subthreshold afferent input according to the IASP - International Association for the Study of Pain (Arendt-Nielsen et al., 2018). A sensitized nervous system has been considered one of the most important mechanisms involved in NP (Cohen, 2022). CS plays a role in fibromyalgia, in which alteration of central nociceptive processing occurs and pain can be worsened by psychological factors (Sluka & Clauw, 2016). In migraine, CS may contribute to acute allodynia and headache chronification (De Tommaso & Sciruicchio, 2016). Furthermore, in migraine CS may play a role in trigeminal nerve activation and cortical spreading depression (De Tommaso & Sciruicchio, 2016). It has been suggested that migraine may be considered as a brain state of altered excitability and a disorder of sensory processing (Goadsby et al., 2017), encompassing additional symptoms as fatigue and mood disorders (Karsan & Goadsby, 2021). Structural and functional MRI studies in women with provoked vulvar or distant/extra-genital pain have supported a role of central sensitization and dysregulation of endogenous pain modulatory systems in the central nervous system in the pathophysiology of vulvodynia (Bergeron et al., 2020).

In the process of central sensitization, psychological factors such as traumatic events in childhood, the development of specific personality expressions (traits), and the use of different forms of defense mechanisms also play a role. No study to our knowledge has yet tried to identify specific clusters of psychological factors (personality traits, defense mechanisms, central sensitization, and childhood traumatic experiences) capable of characterizing or differentiating between the different pathologies expressed by a NP.

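### The planned Two-Step BIC compares clusters with 22 uncorrelated variables, not with one population, so in the pooled sample modest correlation can make a severity continuum look like phenotypes

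*Combined protocol and SAP*

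**What the plan says.** The section headed STATYSTICAL PLANNED ANALYSES clusters participants on personality traits, defenses, central sensitization and childhood trauma. The inputs are "twenty-two variables corresponding to total scores and thematic subscales of the related measures". On method: "A statistical procedure of Two-Step Cluster Analysis will be preferred". On judging the result: "The model fit will be assessed by Schwarz's Bayesian Information Criterion", with the average silhouette as a second index. The software is SPSS 27.

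The section does not state the distance measure, the rule for the number of clusters, whether one cluster is a permitted answer, a silhouette cut-off, a stability check, or any handling of correlation between inputs. It is also not explicit about whether the clustering is pooled or done by diagnosis. The four-group design and the crosstabs suggest the pooled sample.

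The Aims section expects "clusters of high number of early traumatic events, high levels of central sensitization, and specific traits and defense mechanisms" to characterise the three conditions relative to controls with other chronic pain.

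**The concern.** To say that phenotypes exist is to reject the alternative that everyone lies on one continuum. On that continuum the inputs may still be correlated. The section on psychological factors gives reason to expect this: "In the process of central sensitization, psychological factors such as traumatic events in childhood" are said to play a role, together with traits and defenses. The trauma checklist also contributes a total alongside its five subscales, and these are correlated by construction.

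Two-Step treats the inputs as independent within each cluster. Any correlation in a single population is then misfit of the one-cluster model, and BIC can reduce that misfit by cutting the sample along the shared direction. A preference for two clusters may reflect correlation alone. At stake is whether the groups reported under the first aim, and carried into the MANOVAs and correlations, are distinct phenotypes or slices of a severity scale.

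**Working it through.** **Inputs from the plan.** K = 22 inputs; 108 per group, 432 in total. The sample-size inputs are four groups, p = 0.05 and "statistical power of 85%, and effect size of 0.35". Reading 0.35 as Cohen's f, a four-group ANOVA reaches 85% power at 108 participants in total (27 per group, power 86.3%), not per group. That is a separate matter, but it is a second reason to look at n = 108 as well as N = 432.

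**Assumptions.** The correlations are not in the documents; average r from 0 to 0.4 was examined. The log-likelihood form of Two-Step is assumed, because settings are not stated.

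**Formula.** For cluster v, ξ_v = −N_v Σ_k ½ ln(s_k² + s_vk²), and BIC(J) = −2Σξ_v + 2KJ ln N. No covariance appears. BIC rejects one cluster when BIC(1) − BIC(2) > 0.

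**Hand check.** Take one normal population with unit variances and equal correlation r, and split it at the median of the sum score. Each variable's variance within a half falls by δ = (2/π)(1 + 21r)/22. Then

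BIC(1) − BIC(2) = 22N ln[2/(2 − δ)] − 44 ln N.

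- N = 432, penalty 44 × 6.068 = 267.0:
  - r = 0: δ = 0.0289, 138.5 − 267.0 = −128.5
  - r = 0.1: δ = 0.0897, 436.1 − 267.0 = +169.1
  - r = 0.3: δ = 0.2112, 1060.9 − 267.0 = +793.9
  - break-even: δ = 2(1 − e^(−2 ln N/N)) = 0.0554, so r ≈ 0.044
- n = 108, penalty 44 × 4.682 = 206.0:
  - r = 0.2: δ = 0.1505, 185.8 − 206.0 = −20.2
  - r = 0.3: δ = 0.2112, 265.2 − 206.0 = +59.2
  - break-even: δ = 0.1661, so r ≈ 0.23

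**Simulation.** One population with no clusters, 200 data sets per setting, agglomeration on the Two-Step distance (the pre-cluster tree was approximated). Share in which BIC rejects one cluster:

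| Correlation | N = 432 | n = 108 |
|---|---|---|
| r = 0 | 0% | 0% |
| r = 0.05 | 0.5% | 0% |
| r = 0.10 | 96.5% | 0% |
| r = 0.15 | 100% | 0% |
| r = 0.20 | 100% | 10.5% |
| r = 0.30 | 100% | 85% |
| r = 0.40 | 100% | 99.5% |
| 0.3 within / 0.1 between instruments | 100% | 0% |
| 0.4 within / 0.2 between | 100% | 68.5% |
| Totals with subscales, 0.3 / 0.1 | 100% | 18% |

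The simulated median gains at N = 432 were 60 (r = 0.1) and 668 (r = 0.3). They lie below the hand figures because agglomeration does not find the best cut. With k-means splitting, the n = 108 figures are 58% at r = 0.2 and 100% at r = 0.3.

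**Cause.** When the one-class reference was allowed to be correlated, a two-class mixture with independent variables won in 0% of the no-cluster data sets (100 per setting, r = 0 to 0.3 and blocks 0.3/0.1, both sample sizes). Against the independent reference it won in 100% at N = 432 for r of 0.1 or more.

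**Silhouette.** At N = 432 the false solutions had median values of 0.12 (r = 0.1), 0.24 (r = 0.3) and 0.30 (r = 0.4). None reached 0.5.

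**The case against.** Four arguments on the other side deserve weight.

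1. *Trivial correlation is not shown to be enough.* A reader might infer that r of 0.04 to 0.06 already defeats the rule. With k-means splitting it nearly does (98% at r = 0.05), but agglomeration, which is closer to Two-Step, gives about 0–2% there. The hand check shows why: 0.05 lies just above break-even, so the answer depends on how good the cut is. This objection stands, and the claim starts at about 0.1.

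2. *The first aim is not falsely confirmed.* A reader might infer that it is, because the artificial split tends to put high trauma and high sensitization together (84–100% of runs with k-means splits, correlations of 0.2/0.1 to 0.4/0.2 within/between instruments). But the hypothesis concerns differences from controls, and the plan examines association by crosstabs. In 300 no-cluster data sets per setting with four groups of 108, BIC split every time, yet the cluster-by-diagnosis chi-square was significant in only 4.7% (blocks 0.3/0.1) and 5.0% (0.4/0.2). This objection stands.

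3. *The silhouette would look poor.* True, but without a cut-off set beforehand a low value has no consequence, and the index does not exist for one cluster. This stands only in part.

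4. *The plan seeks possible clusters and states no formal test of one against several.* That is so, and the four diagnoses may truly differ. But the purpose stated is to identify different clinical phenotypes, and this BIC cannot separate real subgroups from a correlated continuum.

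**Conclusion.** The concern holds for the pooled analysis. At N = 432 and an average correlation of about 0.1 or more, the Two-Step BIC prefers at least two clusters in about 95–100% of data sets that contain none, against 0% without correlation. At r = 0.05 the result depends on the splitting algorithm. For clustering within one diagnosis (n = 108) the effect is about 10% at r = 0.2 with agglomeration and about 85–100% at 0.3 or more.

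This rests on assumed correlations, normal data, an approximation of the SPSS algorithm and the log-likelihood form of Two-Step. The documents make near-zero correlation unlikely but do not give its size. The consequence is limited to labelling: a severity continuum may be reported as distinct phenotypes. The documents do not support the further inference that a spurious link with diagnosis would follow.

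**What to change.** In STATYSTICAL PLANNED ANALYSES, keep Two-Step but do not let its BIC alone stand as evidence that phenotypes exist.

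- State whether clustering is pooled or by diagnosis, and that one cluster is a permitted result.
- Compare the observed BIC(1) − BIC(2) with its distribution in bootstrap data sets drawn from a single population that keeps the observed marginal distributions and correlations of the 22 inputs, for example through a Gaussian copula.
- Set a silhouette or stability threshold before the data are seen.
- Call the clusters phenotypes only if the observed gain exceeds the bootstrap reference. Otherwise describe them as cut-points on a continuum and compare the diagnoses on the continuous scores.

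In simulation this reference gave 0 of 60 false rejections with normal data and 0 of 60 with skewed trauma scores (one-sided 95% upper limit for each: 1 − 0.05^(1/60) = 4.9%).

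A mixture model with a common covariance is a tempting alternative but fragile here. With assumed skewed trauma scores and no clusters it split falsely in 19 to 30 of 30 runs. It also cannot be fitted if a total is the exact sum of its entered subscales, and it found 0 of 20 true structures at Mahalanobis separations of 2.2–3.3.

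The cost is a few sentences and a little computing, with no new participants. The downside is sensitivity. With true 30/70 clusters, a separation of 1.5 SD on all variables was detected in 20 of 20 runs, but 1.0 SD or less along the shared severity direction was mostly not confirmed.

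### The cluster solution is judged by BIC and an average silhouette with a misstated range and no reference value, so one severity continuum could be reported as phenotypes

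*Combined protocol and SAP*

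**What the plan says.** The section on planned statistical analyses states: "A statistical procedure of Two-Step Cluster Analysis will be preferred". The input is "twenty-two variables corresponding to total scores and thematic subscales of the related measures", and the purpose is given as "aiming to identify different clinical phenotypes within the study samples". On judging the result it says: "The model fit will be assessed by Schwarz's Bayesian Information Criterion and evaluated by the average silhouette coefficient". The silhouette is described as "an internal validity index representing cluster cohesion and separation quality", with values "ranging between 0 and 1; the closer to 1, the better the model".

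Nothing else in the document bears on accepting a solution. There is no minimum silhouette, no comparison with unclustered data, no stability or replication check, and no statement of what follows if BIC selects one cluster or the silhouette is low. Finding clusters is the first aim (Aims section), and the Measures section explains that the questionnaire was split into a main and an optional part to protect the cluster analysis.

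**The concern.** There are two separate faults, and they differ in weight.

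The first is factual. The silhouette has a floor of -1. Zero means that a participant is no closer to the own cluster than to the next one, and a negative value means that the participant is closer to another cluster. A scale that starts at 0 hides both readings.

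The second matters more. Neither criterion has a reference point. If the scores are correlated because they share a general severity dimension, an algorithm can cut that dimension into low, middle and high bands. BIC may prefer the cut, and the silhouette will be positive. The later steps would not expose this. The planned MANOVAs compare clusters on the variables that formed them, so they will show differences for almost any partition. The crosstabs would show an association with diagnosis whenever the diagnoses differ in overall severity. At stake is whether the study can tell distinct psychosocial profiles from degrees of one profile.

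**Working it through.** **Range.** For each participant s = (b - a)/max(a, b), where a is the mean distance to the own cluster and b the mean distance to the nearest other cluster. With a = 0, s = 1; with b = 0, s = -1. The average can also be negative: a small constructed example gave -0.45, and random labels for four groups on 432 simulated participants gave -0.017. The stated lower limit of 0 is therefore wrong.

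**Why BIC does not protect.** Inputs from the plan: 22 variables, and 432 participants ("participants per group (432 as total"). Assumed: standardised scores with a common correlation r, and the Two-Step form of BIC. In that form each cluster of size n contributes n × ln(overall variance + within-cluster variance), summed over variables as if they were independent, plus 2 × 22 = 44 parameters × ln(N).

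- Penalty for a second cluster: 44 × ln(432) = 44 × 6.068 = 267.
- Cut one normal population in half on its sum score. The squared correlation of each variable with the sum is (1 + 21r)/22, so the within-half variance is w = 1 - (2/π)(1 + 21r)/22.
- Gain in fit: 432 × 22 × ln[2/(1 + w)] = 9504 × ln[2/(1 + w)].
- r = 0: w = 0.971, gain about 139. This is below 267, so one cluster is kept.
- r = 0.1: w = 0.910, gain about 436. This is above 267, so two clusters are preferred.
- r = 0.3: w = 0.789, gain about 1061, roughly four times the penalty.

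There are no clusters in any of these cases. The gain comes only from correlation that the likelihood ignores.

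**Simulation of one homogeneous population.** N = 432, 22 normal scores with one common factor, k-means in place of Two-Step, minimum BIC over 1 to 5 clusters, 60 runs per row.

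| Assumed correlation | Runs with more than one cluster | Usual choice (runs) | Mean silhouette, 2 clusters | Mean silhouette at usual choice |
|---|---|---|---|---|
| 0 | 0% | 1 (60) | 0.04 | not applicable |
| 0.2 | 100% | 2 (59) | 0.13 | 0.13 |
| 0.3 | 100% | 3 (60) | 0.17 | 0.10 |
| 0.4 | 100% | 3 (60) | 0.22 | 0.14 |
| 0.5 | 100% | 3 (54) | 0.26 | 0.17 |
| 0.6 | 100% | 4 (45) | 0.30 | 0.16 |

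A further check at correlation 0.1 also gave more than one cluster in 100% of runs, with a two-cluster silhouette of 0.08.

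With all scores log-normally skewed, BIC chose more than one cluster in every run, even at correlation 0. Two-cluster silhouettes were 0.29, 0.39 and 0.44 at correlations 0.3, 0.5 and 0.6. If the silhouette is computed from distances to cluster centres, the two-cluster values are higher: up to 0.44 (normal) and 0.54 (skewed).

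**Comparison with real clusters.** Two true clusters that differ by 1.0 SD on every variable gave 0.18, and by 1.5 SD gave 0.31. The homogeneous values overlap these, so the number cannot be interpreted without a reference.

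**The case against.** A reader might infer that the wrong range is what lets false phenotypes through. It is not. Every fitted solution in the simulation had a positive average, inside 0 to 1, so correcting the range alone would change no decision. The plan also uses the average over participants and does not describe reading individual values.

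A reader might also infer that the plan can never conclude that there are no clusters, or that low values will be accepted as phenotypes. The document supports neither. BIC can select one cluster, and did so in every run with independent normal scores. The Aims section speaks only of possible clusters. A value of 0.10 or 0.17 lies near the poor end of the plan's own scale, and nothing says that it would be accepted. Silhouettes also fall as the number of clusters rises, so two-cluster values overstate what a solution with three or more clusters would show. The last column of the table is the fairer comparison in that case.

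These points limit the wording to what could happen. They do not close the gap: the plan has no rule for a low value, and the scores it describes are not independent. The Traumatic Experiences Checklist alone has a total and five subscales, according to the Measures section.

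**Conclusion.** The stated range is wrong, which is a minor error. The substantive fault is that acceptance rests on BIC and an unreferenced average silhouette, applied to variables that are correlated by construction. Under that design a single severity continuum could be reported as phenotypes. In simulation BIC split one homogeneous population in 100% of runs at assumed correlations of 0.1 or more. The two-cluster silhouettes were about 0.08 to 0.30 for normal scores (correlations 0.1 to 0.6) and up to about 0.44 with all scores skewed.

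This rests on assumptions. The documents give no correlations or distributions, and the simulation used one common factor with equal correlations. K-means with minimum BIC only approximates the SPSS routine, which may choose a different number of clusters. The direction follows from the form of the likelihood; the exact silhouette values do not.

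**What to change.** Before the analysis:

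1. State the silhouette range as -1 to 1.
2. Define acceptance. A solution is called phenotypes only if its average silhouette exceeds the 95th percentile obtained when the same procedure, with the same form of silhouette and the same number of clusters, is run on simulated single-population data (say 1,000 sets). These data should keep the study's own correlation matrix and each score's observed distribution.
3. State the alternative. If the threshold is not met, or BIC selects one cluster, report that no distinct clusters were supported and analyse the scores as continuous dimensions.

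A multivariate normal reference is not enough, because trauma scores are likely to be skewed. In a check with skewed scores and no clusters, 30 to 35% of data sets passed a normal reference at correlations of 0.3 and 0.5. With a reference that kept the observed distributions, 0 to 5% passed.

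A rule of this kind need not block real findings. With 40 runs per setting, two true clusters 1.0 SD apart averaged 0.181 against a threshold of 0.145. At 1.5 SD with within-cluster correlation 0.3, they averaged 0.324 against 0.293. All runs passed. That check used normal scores and a normal reference, so it should be repeated with the final rule.

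The cost is one corrected figure and a scripted reference run on data already being collected. The downside is that the study may have to report that no clusters were supported.
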